1.0 Objectives

Primary objectives

The primary objective is to assess complete response (CR) rate and overall survival

Secondary objectives

The secondary objectives are to assess duration of response, relapse-free survival, and the safety profile

2.0 Background

Myelodysplastic syndromes (MDS) are a heterogeneous group of disorders characterized by progressive pancytopenia due to impaired cellular differentiation and increased apoptosis, with a tendency to convert to acute leukemia [1]. The disease typically affects individuals over 65 years of age, and it is thought to result from multiple mutations affecting the hematopoietic stem cell. There is a wide clinical spectrum of MDS ranging from moderate anemia with normal neutrophil and platelet counts, to frank leukemia with a clinical course that can range from a few months to many years. Treatment options are limited. Only bone marrow transplantation offers a cure although there are significant treatment-related adverse events that can result from this procedure [2].

In the U.S. there are currently 2 drugs approved for the treatment of (non 5q-) MDS: azacitidine and decitabine (referred to collectively as hypomethylating agents). Both drugs are active although the objective response rates they produce are low [3]. In the case of azacitidine a recent large randomized study demonstrated a survival benefit for azacitidine-treated patients compared to those who received conventional care (including best supportive care) [4]. Although either of these drugs are among the best available outside clinical trials, they are not curative and typically patients relapse either on therapy or shortly after completion of therapy. SGI-110 is a second generation hypomethylating agent with significantly increased activity than azacitidine or decitabine and is being investigated at MD Anderson Cancer Center (MDACC Protocol # 2010-0615).

These patients who have either not responded to or relapsed from treatment with hypomethylating agents carry a dismal prognosis with a median survival of less than 6 months, a 1-year survival probability of less than 30% and a likelihood of response to conventional therapies (e.g. cytarabine of around 20%) [5]. Hence, new approaches are needed for patients in this situation.

Clofarabine is a second generation purine nucleoside analog that incorporates two halogen atoms, chlorine and fluorine, resulting in resistance to both adenosine deaminase degradation and phosphorolysis [6]. Studies of clofarabine (both i.v. and p.o.) have demonstrated activity in patients with higher risk MDS [7]. In addition, we have previously shown the feasibility and efficacy of the combination of lower dose clofarabine (30 mg/m²/day) with low-dose cytarabine in patients with high-risk MDS and acute myeloid leukemia (AML), which was more active than single agent clofarabine [8].

Here we propose to take this approach of the combination of clofarabine with low-dose cytarabine and use this combination to treat patients with higher-risk MDS who have failed to respond to hypomethylating agents. These patients are facing a huge unmet medical need.

3.0 Background Drug Information

3.1 Clofarabine

Clofarabine is FDA approved for children with relapsed/refractory acute lymphoblastic leukemia and

therefore commercially available.

Clofarabine is formulated at a concentration of 1mg/mL in sodium chloride (9mg/mL), United States Pharmacopeia (USP) or European Pharmacopeia (EP) and water for injection, USP or EP, quantity sufficient (qs) to 1 mL. Clofarabine is supplied in 20-mL flint vials contain 20 mL (20 mg) of solution. The pH range of the solution is 4.5 to 7.5. The solution is clear and practically colorless, is preservative free, and is free from foreign matter.

Vials containing undiluted clofarabine should be stored at room temperature (15° to 25° C; 59° to 77° F). Ongoing shelf-life stability studies indicate that clofarabine is stable for 36 months at 25°C and 60% relative humidity and for 6 months at 40°C (+/- 2°C) and 75% (+/- 5%) relative humidity.

Clofarabine for injection should be filtered through a sterile 0.2 microM syringe and then further diluted with 0.9% sodium chloride injection USP or EP for a final concentration of 0.15 to 0.4 mg/mL prior to IV infusion. The resulting admixture may be stored at room temperature, but must be used within 24 hours of preparation. Clofarabine will be administered as a 1- to 2-hour IV infusion as tolerated. To prevent drug incompatibilities, no other medications should be infused concurrently through the same IV lines as clofarabine. Also, no blood products should be administered at the same time as clofarabine.

3.2 Cytarabine (Ara-C)

Cytarabine is available commercially.

Cytarabine is a deoxycytidine analog that is metabolized to cytarabine triphosphate, a substance that inhibits DNA polymerase. It is S phase specific, and thus affects DNA synthesis. It has an initial plasma half-life of about 15 minutes, with a secondary phase of about 2 hours, and is rapidly catabolized by hepatic cytidine deaminases to Ara-U.

Cytarabine injection, an antineoplastic is a sterile solution of cytarabine for intravenous administration. Each mL contains 20 mg cytarabine in 100 mg (20 mg/mL) single dose vials and 100 mg cytarabine in 2 g (100 mg/mL) single dose vial.

Cytarabine comes as 20 mg/mL (5, 25 and 50 mL vials) and 100 mg/ml solutions (20 mL vial), in addition to several vial sizes of powder for solution (100 mg, 500 mg, 1 g, 2 g).

Cytarabine to be prepared as per institutional standards based on product availability.

3.3 Expected Toxicities

Myelosuppression, nausea/vomiting, diarrhea, mucositis, skin rash with blisters (particularly hand-foot syndrome), Steven-Johnson's syndrome, fatigue, mental status changes/coma, allergic reactions (including fever, muscle aches, edema, dyspnea), congestive heart failure, conjunctivitis, and anorexia. Pancreatitis, liver failure, kidney failure. Infections.

Autoimmune reactions (antiplatelet antibodies, erythema nodosum) and/or chemical imbalances in the blood, lethargy, malaise, asthenia, alopecia, peritonitis, anorexia, stomatitis/pharyngitis, hyperbilirubinemia, increase of SGPT and/or SGOT, abdominal pain or cramping.

3.4 Drug Supply

Clofarabine is approved by the FDA for use in pediatric acute lymphoblastic leukemia and will be used off label in higher-risk MDS in this study. Ara-C (cytarabine) is approved for use in patients with AML but will

be used for patients with higher-risk MDS in this study. Neither clofarabine nor cytarabine will be provided free of charge during the study.

4.0 Patient Eligibility

Inclusion:

- 1) Age \geq 18 years.
- 2) Diagnosis of MDS confirmed within 10 weeks prior to study entry according to WHO or FAB criteria. Patients are either not eligible for or choose not to proceed with a stem cell transplant.
- 3) MDS classified as follows: RAEB-1 (5%-9% BM blasts); RAEB-2 (10%-19% BM Blasts); CMML (5%-19% BM blasts); RAEB-t (20%-29% BM blasts) AND/OR by IPSS: intermediate-2 and high risk patients.
- 4) No response, progression, or relapse (according to 2006 IWG criteria; see section 8 for details) following at least 4 cycles of either azacitidine or decitabine, or following at least 2 cycles of SGI-110, which were completed within the last 2 years - AND/OR - intolerance to azacitidine, decitabine, or SGI-110 defined as drug-related \geq grade 3 hepatic or renal toxicity leading to treatment discontinuation during the preceding 2 years.
- 5) Eastern Cooperative Oncology Group (ECOG) performance status of \leq 2.
- 6) Willing to adhere to and comply with all prohibitions and restrictions specified in the protocol.
- 7) Patient (or patient's legally authorized representative) must have signed an informed consent document indicating that the patient understands the purpose of and procedures required for the study and is willing to participate in the study.

Exclusion:

- 1) Uncontrolled intercurrent illness including, but not limited to, symptomatic congestive heart failure, unstable angina pectoris, or cardiac arrhythmia.
- 2) Active infection not adequately responding to appropriate antibiotics (i.e. ongoing temperatures of \geq 38 degree Celsius).
- 3) Total bilirubin \geq 1.5 mg/dL and not related to hemolysis or Gilbert's disease. Patients with total bilirubin \geq 1.5 mg/dL to 3 mg/dL are eligible if at least 75% of the bilirubin is indirect.
- 4) Alanine transaminase (ALT/SGPT) or aspartate transaminase (AST/SGOT) \geq 2.5 x the upper limit of normal.
- 5) Serum creatinine $>$ 1.5 mg/dL.
- 6) Female patients who are pregnant or lactating.
- 7) Patients with reproductive potential who are unwilling to following contraception requirements (including condom use for males with sexual partners, and for females: prescription oral contraceptives [birth control pills], contraceptive injections, intrauterine devices [IUD], double-barrier method [spermicidal jelly or foam with condoms or diaphragm], contraceptive patch, or surgical sterilization) throughout the study.
- 8) Female patients with reproductive potential who do not have a negative urine or blood beta-human

chorionic gonadotropin (beta HCG) pregnancy test at screening.

9) Patients receiving any other concurrent investigational agent or chemotherapy, radiotherapy, or immunotherapy.

10) No prior treatment with cytarabine or clofarabine. Prior hydroxyurea for control of leukocytosis or use of hematopoietic growth factors (eg, G-CSF, GM-CSF, procrit, aranesp, thrombopoietins) is allowed at any time prior to or during study if considered to be in the best interest of the patient.

11) Psychiatric illness or social situation that would limit the patient's ability to comply with study requirements.

5.0 Treatment Plan

5.1 Study Treatment

Patients may receive up to 3 cycles of induction therapy and up to 12 cycles of consolidation. Treatment will be terminated if patients exhibit evidence of treatment failure, disease progression, experience clinically significant toxicity, or the investigator determines that discontinuation of treatment is in the best interest of the patient.

Patients will be treated with study drugs based on a calculation determined from the patient's BSA. Body surface area (BSA) will be calculated before each cycle and will be based on the patient's height (measured at baseline) and weight (measured each cycle).

Patients will be instructed to self-administer cytarabine at home and return unused drug to be handled and processed by the dispensing pharmacy.

In order to lower the risk of pregnancy, patients of child bearing potential must agree to use acceptable forms of birth control until at least 8 weeks after the last dose of therapy is administered. If patients are already using birth control, they must check with the study doctor or a member of the study staff to make sure that it is considered one of the acceptable forms to use in this study. Examples of effective birth control include condoms or diaphragms with spermicidal jelly, and birth control methods that are taken by mouth, injected, or implanted.

Except for the first cycle, treatment can be administered at MDACC or through the supervision of the home physician.

5.1.1 Induction

Clofarabine 10 mg/m² as a 1-2 hours i.v. infusion. daily for 5 days (days 1-5)

Cytarabine 20 mg s.c. twice daily for 7 days (days 1-7)

Cytarabine should be administered 3 to 6 hours following the start of the clofarabine infusions.

Cycles are repeated every 4 to 8 weeks depending on resolution of toxicities. No dose reductions, delays, or modifications are required for hematologic toxicities during the induction cycles. It is assumed that low counts at diagnosis are due to involvement by the disease process and require therapy for improvement. Patients who receive repeated induction cycles have persistent disease and thus no recovery of hematologic parameters can be expected.

Patients can receive up to a maximum of 3 induction cycles as long as they have stable disease and do not progress. If patients have not achieved at least a hematologic improvement after three cycles, they should be taken off study. Patients with at least hematologic improvement can continue the consolidation. Patients with any response less than CR or CRp before completion of three induction cycles can complete all three induction cycles in an effort to maximize their response prior to moving on with the consolidation if this is considered in the best interest of a particular patient.

5.1.2 Consolidation

Clofarabine 10 mg/m² as a 1-2 hours i.v. infusion daily for 3 days (days 1-3)
Cytarabine 20 mg s.c. twice daily for 5 days (days 1-5)

Cytarabine should be administered 3 to 6 hours following the start of the clofarabine infusions.

Cycles are repeated every 4 to 8 weeks depending on hematopoietic recovery and resolution of toxicities. The maximum number of consolidation cycles is 12. Patients who continue with treatment after a delay for any reason other than toxicity or adverse event must restart treatment by Day 84 after Day 1 of the previous cycle. Patients can start after day 84 if discussed with and approved by the Principal Investigator.

5.1.3. Supportive Measures During Treatment

Necessary supportive measures for optimal medical care are to be given throughout the study as indicated by the treating physician's assessment of the patient's medical need and by the institutional guidelines. Administration of antiemetics during drug administration is strongly recommended.

It is recommended that the patient's fluid status and hepatic and renal function be carefully monitored daily during the drug administration period.

Management of Capillary Leak Syndrome

In pediatric studies, during or shortly after IV clofarabine administration a few patients developed signs and symptoms consistent with capillary leak syndrome. In these heavily pretreated patients, it has been difficult to separate potential drug-related cases of capillary leak syndrome from concurrent medical conditions such as infections/sepsis, progressive disease, or other underlying problems resulting from prior antileukemic therapies.

For these reasons, during and after each dose of clofarabine investigators should assess patients for the onset of the following signs or symptoms \geq grade 2:

- Tachypnea or other evidence of respiratory distress;
- Unexplained hypotension; and/or
- Unexplained tachycardia

If one or more of these signs or symptoms occurs during study drug infusion, clofarabine administration is to be interrupted or held as clinically indicated. It is recognized that the total infusion time for this clofarabine dose in this circumstance may exceed 1 hour. Thus, if the patient's condition stabilizes or improves, clofarabine administration may resume. Pretreatment with steroids (e.g. hydrocortisone 100 mg/day or its equivalent or dexamethasone 20 mg/day as part of an anti-emetic regimen) is recommended for all subsequent doses during the remainder of that treatment cycle and for all subsequent treatment cycles.

5.2 Dose Modifications

Dose modifications can be made for one drug only if the investigator is reasonably confident that the toxicity relates to that particular drug. If that distinction cannot be made, the doses of both drugs should be modified.

Missed doses of clofarabine and/or cytarabine can be made up on subsequent days if felt to be in the best interest of the patient.

5.2.1 Hematologic (Blood/Bone Marrow) Toxicity

No dose reductions, delays, or modifications are required for hematologic toxicities during the induction cycles. It is assumed that low counts at diagnosis are due to involvement by the disease process and require therapy for improvement. Patients who are considered for reinduction have persistent disease and thus no recovery of hematologic parameters can be expected in the absence of further therapy.

Patients who achieve a CR/CRp should receive the consolidation cycles no sooner than 28 days from Day 1 of the previous cycle, provided the ANC has recovered to $\geq 1.0 \times 10^9/L$ and the platelet count $\geq 50 \times 10^9/L$ (in case of CR). For patients in CRp where the platelet count by definition has not recovered, no limits are set to continue. If the peripheral count recovery is delayed beyond 42 days from Day 1 of the prior cycle and the delay is presumed to be secondary to the therapy, the study drug doses for the next cycle should be reduced by 25%.

5.2.2 Non-Hematologic Toxicity

Patients who experience a > grade 1 drug-related non-hematologic toxicity or drug-related asymptomatic grade 2 elevations of creatinine, bilirubin, amylase, lipase during any week of treatment should have clofarabine held until recovery to grade 1 before starting treatment. Grade 3 drug-related toxicities that result in delays or omissions must resolve to grade 1 before starting treatment. Dose omissions due to toxicities that occur during the treatment can be made up as per the treating physician's discretion and if this is felt to be in the best interest of the patient.

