5.2.2.2 Non-infectious, drug-related

a) First or second occurrence of a drug-related \geq grade 3 toxicity:

If toxicity recovers to Grade 1 within 35 days from the onset of the toxicity: study therapy is to be restarted at 25% reduction with no alteration in schedule from the previous doses for all subsequent cycles.*

If toxicity **does not** recover to Grade 1 within 35 days from the onset of toxicity: the patient should not receive additional study drug.*

* Excludes NCI CTC grade 2 alopecia and \geq grade 3 anorexia, transient elevations in hepatic transaminases or alkaline phosphatase based on institutional normals without clinical significance, and nausea/vomiting, diarrhea or mucositis that resolves (with or without supportive care) to < grade 2 within 72 hours of onset to grade 3.

b) 3rd Occurrence of a drug-related non-infectious event(s): Grade 3 toxicity:

The patient should not receive any additional treatment.

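### The rules for non-hematologic toxicity give two different instructions in two situations (resuming clofarabine after an infusion-time sign, and holding one drug or both), and no section says which prevails

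*Combined protocol and SAP*

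**What the plan says.** Four sections of the protocol bear on the same events.

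- **5.2.2** sets the general hold. Its trigger is "Patients who experience a > grade 1 drug-related non-hematologic toxicity or drug-related asymptomatic grade 2 elevations of creatinine, bilirubin, amylase, lipase", in any week of treatment. Such patients "should have clofarabine held until recovery to grade 1 before starting treatment". It adds: "Grade 3 drug-related toxicities that result in delays or omissions must resolve to grade 1 before starting treatment". It also says: "Dose omissions due to toxicities that occur during the treatment can be made up as per the treating physician's discretion". Cytarabine is not mentioned, and no toxicity is exempted.
- **5.1.3** deals with possible capillary leak. Respiratory distress, unexplained hypotension and unexplained tachycardia are looked for at grade 2 or higher, and clofarabine is interrupted or held if one occurs during the infusion. Then: "Thus, if the patient's condition stabilizes or improves, clofarabine administration may resume".
- **5.2** lets one drug be modified only when the investigator is reasonably confident that this drug caused the toxicity. "If that distinction cannot be made, the doses of both drugs should be modified".
- **5.2.2.2(a)** covers a first or second drug-related event of grade 3 or higher. If it recovers to grade 1 within 35 days, "study therapy is to be restarted at 25% reduction with no alteration in schedule from the previous doses for all subsequent cycles". If it does not, no more study drug is given. A footnote to both actions begins "Excludes NCI CTC grade 2 alopecia" and goes on to list certain anorexia, liver-enzyme, gastrointestinal and mucosal events.

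**The concern.** A treating physician who follows the text exactly can reach two different actions for one event, depending on which section is open. For an infusion-time sign this is a safety matter: one section lets the drug restart on stability alone, and the other requires recovery to grade 1 first. For an event that cannot be attributed to one drug, the question is whether cytarabine continues.

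The written rule has to stand on its own here. Section 5.1 allows every cycle after the first to be supervised by the home physician, and patients give themselves cytarabine at home. If physicians resolve the conflict differently, the exposure behind the CR rate also varies for reasons that the plan does not control.

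**Working it through.** No figure in the plan depends on this wording, so the check is a comparison of the sections, with a small dose illustration at the end.

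| Section | Event | Drug named | Condition for giving drug again |
|---|---|---|---|
| 5.1.3 | Listed signs, grade 2 or higher, during infusion | Clofarabine | Stable or improved |
| 5.2 | Any toxicity | One drug if attributed, otherwise both | None stated |
| 5.2.2 | Drug-related, non-hematologic, above grade 1 | Clofarabine | Grade 1 |
| 5.2.2.2(a) | Drug-related, non-infectious, grade 3 or higher | Study therapy | Grade 1 within 35 days, then 25% less; otherwise none |

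**Step 1: infusion-time sign.** Take drug-related hypotension that settles at grade 2. It meets 5.1.3 (grade 2 or higher) and 5.2.2 (above grade 1). Under 5.1.3 clofarabine may resume; under 5.2.2 it stays held, because grade 1 has not been reached. If the event was grade 3 or higher, 5.2.2.2(a) also applies and leads to a reduction or to no further drug. Section 5.1.3 mentions neither.

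**Step 2: one drug or both.** Take a drug-related grade 2 event that cannot be attributed to one drug. Section 5.2 modifies both; 5.2.2 holds clofarabine and is silent on cytarabine. Now take an event confidently attributed to cytarabine. Section 5.2 allows a change to cytarabine alone; 5.2.2 still holds clofarabine.

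**Step 3: the two clauses of 5.2.2.** Above grade 1 means grade 2 or more. Asymptomatic grade 2 elevations of the four laboratory values are a subset of that and get the same action. The clause is redundant, which suggests an error in the threshold or a lost exception. The separate grade 3 sentence also releases at grade 1, so it agrees with the hold.

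**Step 4: the footnote.** Grade 2 alopecia cannot fall under a rule that starts at grade 3, so that exclusion has no effect where it stands. Section 5.2.2, where grade 2 does matter, has no exclusions. Alopecia is among the expected toxicities in section 3.3.

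**Step 5: illustration.** Inputs are from section 5.1.1. Planned clofarabine per induction cycle: 10 mg/m² × 5 = 50 mg/m². Planned cytarabine: 20 mg × 2 × 7 = 280 mg. Assume an event after the day 2 doses, an in-cycle hold, no recovery to grade 1 in that cycle, and no make-up doses. Given by then: 10 × 2 = 20 mg/m² clofarabine (20/50 = 40%) and 20 × 2 × 2 = 80 mg cytarabine.

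| Text followed | Clofarabine (mg/m²) | Cytarabine (mg) |
|---|---|---|
| 5.2.2 literally | 20 of 50 | 280 of 280 |
| 5.2.2 hold, with 5.2 extending the change to both drugs | 20 of 50 | 80 (if modified means held) to below 280 |
| 5.1.3 resumption (capillary-leak signs only) | up to 50 of 50 | not addressed |

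**The case against.** The strongest reply is that the sections have different scopes.

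- Section 5.1.3 concerns an interruption within one infusion, is permissive, and could be read as a specific rule that overrides the general one. It calls hypotension and tachycardia unexplained and says that drug-related cases are hard to separate from infection or progression, whereas 5.2.2 requires drug-relatedness. This narrows the overlap to signs judged drug-related but does not remove it. No precedence is stated, and permission to resume remains at odds with a required hold.
- The 5.2.2 hold ends with a reference to starting treatment, so it might govern only the start of a cycle. Yet its trigger is toxicity in any treatment week, and it deals with doses omitted during treatment. Both readings are open.
- Section 5.2.1 lists reductions, delays and modifications separately, so a hold might not be a modification; and 5.2.2's silence on cytarabine might leave that drug to 5.2. Against this, 5.2.2 sits under the heading Dose Modifications, and nothing says that the two are to be combined.

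A reader might also infer more than the text supports:

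- That the laboratory clause contradicts the first half of 5.2.2. It changes no action.
- That the footnote contradicts the hold. It limits reduction and discontinuation, so a physician can hold to grade 1 and then not reduce. That it was meant to reach 5.2.2 is inference.
- That grade 3 hypotension settling at grade 2 brings the 25% reduction. That branch requires recovery to grade 1 within 35 days; without it the discontinuation branch applies.
- That an early hold costs 60% of a cycle's clofarabine. Sections 5.2 and 5.2.2 both allow make-up doses.
- That the conflict would arise often. Section 3.3 gives neither grades nor frequencies, and 5.1.3 speaks only of a few pediatric patients.

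**Conclusion.** Two conflicts stand.

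(a) A drug-related infusion-time sign that stabilises at grade 2 or higher may be followed by more clofarabine under 5.1.3 and must be followed by a hold under 5.2.2. At grade 3 or higher, 5.2.2.2 adds consequences that 5.1.3 does not mention. This assumes that the sign is judged drug-related and that the 5.2.2 hold reaches doses within a cycle.

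(b) Section 5.2.2 holds clofarabine alone where 5.2 calls for both drugs or allows a change to cytarabine only. This assumes that a hold is a dose modification.

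The redundant clause and the inert alopecia exclusion are drafting faults, not further conflicts. The effect on exposure is not fixed: it depends on time to recovery and on discretionary make-up doses, and the illustration shows the extreme. An effect on the CR rate is possible but cannot be sized from the documents. The stopping boundaries and Tables 1 to 4 in section 10.0 do not use these rules, so no operating characteristic is affected. The point should be corrected because a safety-relevant event receives contradictory instructions; it does not undermine the design.

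**What to change.** Reconcile sections 5.1.3, 5.2, 5.2.2 and 5.2.2.2 so that each event leads to one instruction. The text should state:

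- which section governs a drug-related infusion-time event of grade 2 or higher;
- whether the 5.2.2 hold covers one drug or both, and whether it applies within a cycle or only at its start;
- what grade threshold 5.2.2 intends, with the redundant clause removed or corrected to match;
- which rule the exclusion footnote modifies.

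The clinical team decides the content. No threshold, dose or rule is proposed here, and neither 5.2 nor 5.2.2 is preferred. The cost is a wording amendment of about one page, with no added visits, procedures or patients.

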6.0 Pretreatment evaluation

History and physical.

CBC with differential and platelets, chemistry profile (total bilirubin, serum creatinine, SGPT or SGOT, uric acid, LDH, potassium, magnesium) within 14 days of therapy start.

Bone marrow aspirate and/or biopsy within 28 days of therapy start. The bone marrow evaluation must include cytogenetic studies except for situations where cytogenetic analysis was not added to a bone marrow aspirate and/or biopsy and the stage/prognostic group of the MDS can be ascertained as higher risk based on the available information (eg, blasts and/or degree of cytopenias).

Pregnancy (urine or blood) test for women of childbearing potential within two weeks of start of therapy. Child bearing potential is defined as not post-menopausal for 12 months or no previous surgical sterilization.

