7.0 Evaluation During Study

CBC with differential and platelet counts at least weekly while on therapy and every 4 to 8 weeks thereafter as long as on study. No differential is needed if the WBC is $< 1.0 \times 10^9/L$.

Chemistry profile (at least creatinine, SGOT or SGPT, total bilirubin, potassium, magnesium) every two weeks while on therapy, then every 4 to 8 weeks as long as on study.

Bone marrow aspirate and/or biopsy at the end of course 1 (day 28 +/- 7 days). If a patient is not in remission at this point, further bone marrow aspirate and/or biopsy can be scheduled as per the investigator's discretion and mandated by the development of the peripheral blood counts.

No repeat bone marrow is necessary if non-response or progressive disease can be unequivocally diagnosed from peripheral blood tests, or, in patients with a WBC \leq 0.3 if the bone marrow test is considered non-contributory by the investigator at any time point.

Follow up marrow tests should include cytogenetic analysis for those patients who had abnormalities prior to therapy start.

Repeat physical examination (problem focused) prior to administration of each course

After completion of therapy and as long as still on study, patients will return to MD Anderson Cancer Center for repeat physical examination (problem focused), repeat CBC with differential and platelet count, and chemistry profile (at least creatinine, SGOT or SGPT, total bilirubin, potassium, magnesium) every 6 months (+/- 2 months). A CBC with differential and platelet count should be checked every one to two months, but these blood tests may be done locally.

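### The clofarabine hold for asymptomatic grade 2 amylase or lipase rises has no scheduled test behind it, so it applies only if a physician chooses to order the enzymes

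*Combined protocol and SAP*

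**What the plan says.** Section 5.2.2 has two routes to a clofarabine hold. The general one covers "Patients who experience a > grade 1 drug-related non-hematologic toxicity". The specific one covers "drug-related asymptomatic grade 2 elevations of creatinine, bilirubin, amylase, lipase during any week of treatment should have clofarabine held". Either way, clofarabine waits for recovery to grade 1.

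For drug-related toxicity of grade 3 or more that recovers to grade 1 within 35 days, Section 5.2.2.2 adds that "study therapy is to be restarted at 25% reduction with no alteration in schedule". Without recovery in that time, study drug ends. A third grade 3 occurrence also ends treatment.

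The laboratory requirements are set elsewhere:

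- Section 6.0, baseline: "chemistry profile (total bilirubin, serum creatinine, SGPT or SGOT, uric acid, LDH, potassium, magnesium) within 14 days of therapy start".
- Section 7.0, on therapy: "Chemistry profile (at least creatinine, SGOT or SGPT, total bilirubin, potassium, magnesium) every two weeks while on therapy". The same five-item minimum applies at the six-monthly visits after therapy.
- Section 5.1.3 recommends that "fluid status and hepatic and renal function be carefully monitored daily during the drug administration period".

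Section 3.3 lists among the expected toxicities "Pancreatitis, liver failure, kidney failure. Infections". Section 5.1 states: "Except for the first cycle, treatment can be administered at MDACC or through the supervision of the home physician".

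**The concern.** A rule that acts on an asymptomatic laboratory value works only if the value is measured. Amylase and lipase are named as triggers, yet no laboratory list asks for them. A site that follows the schedule exactly can therefore re-dose a patient whom Section 5.2.2 says to hold, or give full dose to a patient whom Section 5.2.2.2 says to reduce or stop.

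Every one of these actions also requires the event to be drug-related. With no baseline enzyme value, a rise that was present before treatment is hard to tell from a new one.

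What is at stake is patient safety and consistent dosing. There is a smaller effect on toxicity data: an asymptomatic enzyme rise of grade 3 or more enters the Section 10 toxicity count only where someone happened to order the test.

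**Working it through.** The plan gives no figure to reproduce. The check sets the triggers against the schedules and then tests whether the existing draw interval would be enough.

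**1. Coverage of the four named triggers**

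| Analyte in 5.2.2 | 6.0 baseline (7 items) | 7.0 on therapy (5-item minimum) | 7.0 after therapy (5-item minimum) | 5.1.3 daily recommendation |
|---|---|---|---|---|
| Creatinine | yes | yes | yes | within renal function |
| Bilirubin | yes | yes | yes | within hepatic function |
| Amylase | no | no | no | no |
| Lipase | no | no | no | no |

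Scheduled: 2 of 4. Not scheduled at any time point: 4 − 2 = 2. In the supplied text the two enzymes appear only in Section 5.2.2.

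**2. What is missed and what is not**

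- Symptomatic pancreatitis above grade 1 and judged drug-related: the general part of 5.2.2 applies without any enzyme schedule. Not missed.
- Asymptomatic grade 2 enzyme rise: both parts of 5.2.2 require a hold, but only a test can reveal it. Missed unless ordered.
- Asymptomatic enzyme rise of grade 3 or more: the 5.2.2.2 footnote exempts certain transient transaminase and alkaline phosphatase elevations but not amylase or lipase, so the reduction or stop applies. Missed unless ordered.

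**3. Would the two-weekly interval suffice if the enzymes were added?**

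Inputs: shortest cycle 4 weeks = 28 days, so the earliest next Day 1 is Day 29; clofarabine on days 1–5 in induction (5.1.1) and days 1–3 in consolidation (5.1.2); one draw every 14 days. Assumption: the on-therapy period in 7.0 means the whole cycle.

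- Induction, days after the last dose and before Day 29: days 6–28, so 28 − 5 = 23 days.
- Consolidation: days 4–28, so 28 − 3 = 25 days.
- Both exceed 14 days, so at least one draw falls between the last dose and the next Day 1. Longer cycles only widen the window.

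That shows a draw exists, not that it is current. With draws 14 days apart and no fixed starting day, the last draw before Day 29 can fall anywhere from Day 15 to Day 28. Its age at re-dosing is then between 29 − 28 = 1 day and 29 − 15 = 14 days. The dosing windows of 5 and 3 days are also shorter than 14 days, so a draw need not fall within dosing at all. Draws on Days 8 and 22, for example, miss induction dosing entirely. The enzymes need to be added, and one draw also needs to be tied to Day 1.

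**The case against.** The strongest reply has four parts.

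*Section 5.2.2 says what to do once an abnormality is known; it is not a screening plan.* The Section 7.0 list is an explicit minimum, and supportive care is left to the treating physician and institutional guidelines. This stands as far as it goes: a physician may order the enzymes, and local practice may already include them. A reader might infer that the enzyme hold can never operate; the documents do not support that. They do show that nothing requires the test. That treatment under a home physician makes ordering less uniform is a possibility, not something the documents establish.

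*Other unscheduled analytes are named.* Alkaline phosphatase is in the 5.2.2.2 footnote but in neither profile. True, but there it is part of an exemption, so failing to measure it leaves no required action undone.

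*Screening has a price.* This stands. Because the footnote does not exempt the enzymes, routine testing can produce 25% reductions for all later cycles, or an end to treatment, in patients without symptoms. Section 2.0 puts median survival in this population below 6 months, so lost dose matters. Section 10 also counts grade 3 or greater non-hematologic events toward stopping (6 of 10, 8 of 15 and so on), so more testing may raise that count.

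*The enzymes could simply be deleted from 5.2.2.* That would remove the visible mismatch but not the gap. A drug-related grade 2 enzyme rise would still fall under the general part of 5.2.2, and 5.2.2.2 would still apply from grade 3.

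**Conclusion.** The point holds for asymptomatic amylase and lipase rises: two of the four analytes named in the hold rule have no scheduled measurement, at baseline or later. It is a modest safety and dosing-consistency defect, and it merits an amendment because the remedy is cheap.

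Two stronger readings should be resisted. A reader might infer that pancreatitis goes unmanaged; the general part of Section 5.2.2 covers it when symptomatic. A reader might also infer that the efficacy results or the stopping boundaries are compromised; the CR and overall survival analyses and the sample size do not depend on these enzymes, and the toxicity boundaries are fixed numbers that do not move. Only the count compared with those boundaries could shift, and only through events of grade 3 or more.

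The documents give no rate of asymptomatic enzyme elevation, so neither the number of patients affected nor any change in the chance of a toxicity stop can be calculated. The conclusion assumes that Appendices D and E, which are not in the supplied text, set no laboratory schedule; Section 11.0 cites them only for recording and listing adverse events.

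**What to change.** Add amylase and lipase to the Section 6.0 baseline profile and to the Section 7.0 two-weekly on-therapy profile, on draws already taken. State in Section 7.0 that one of those draws is timed shortly before Day 1 of each cycle, so that a current value is available when re-dosing is decided. Blood counts are already required at least weekly on therapy, so the timed draw can share one of those.

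Cost: a wording change in two sections, two more analytes per chemistry draw and no new procedure. The consequences to accept openly are some incidental findings, possible additional holds or 25% reductions under Section 5.2.2.2, and possibly a few more grade 3 or greater events counted toward the unchanged toxicity boundaries in Section 10.
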